**Date**

Medical Monitor name and contact information can be found in [Appendix 2](#).

PROTOCOL AMENDMENT SUMMARY OF CHANGES TABLE

Table 1 Document History

Document	Date	Substantial	Region
Amendment 1	09 October 2018	Yes	US
Original Protocol	17 July 2018	-	-

Amendment 1 (09 October 2018)

Overall Rationale for the Amendment:

During creation of the electronic case report forms (eCRFs) on otoscopy assessment, a discrepancy was noted in the way the assessments are described in the eCRF versus the protocol. It was thus decided to amend the description in the protocol to match the eCRF. Additionally, during the eCRF creation, updates to the section on nasal and epipharynx endoscopy, and audiology pure tone hearing test was also updated in the protocol. Moreover, discussions with IQVIA biostatisticians and the study center led to the update of the randomization procedure, the number of days residency in the study center and clarity on assessments to be performed in the case of early termination of the study. Due to logistical reasons, the telephonic study exit visit at Day 30 was removed and Day 21 will now be the study exit visit.

Table 2 Description of Changes in Amendment

Section # and Name	Description of Change	Brief Rationale
Synopsis – Overall design, Section 4.1 Study Design and Section 6.3.1 Study Treatment Kit	Removal of stratification by gender.	Per the protocol, randomization is to be stratified by gender within each of the 2 cohorts (Cohorts A and B) and subjects are to be randomized in 4:1 ratio to active:placebo within each cohort. After further discussion with IQVIA biostatisticians and the Sponsor, it was agreed that gender stratification within a 4:1 randomization scheme would be problematic. Thus, gender stratification is removed from the protocol.
Section 1.3 Schedule of Activities	Addition of early termination (EaT) assessments to align with the Day 21 study exit visit.	Per the protocol, no assessments are specified for cases where a subject has been treated but wants to discontinue early from the study. IQVIA, in consultation with the Sponsor, discussed and agreed that as a standard, when subjects discontinue early, if possible, they should complete all study procedures required at the study exit visit. Thus, the protocol has been amended to reflect this.

Section # and Name	Description of Change	Brief Rationale
Synopsis – Overall design, Section 1.2 Schema, Section 1.3 Schedule of Activities and Section 4.1 Study Design	Removal of the option for subjects to leave the study center on the evening of Day 14 after all the assessments have been completed.	Previously, the protocol gave the option for subjects to leave the study center on Day 14 after all the assessments have been completed. However, in consultation with the study center it was decided that the timing of the last dose administration on Day 14 (23:00) was too late and that most subjects would opt to stay the night and leave the study center on the morning of Day 15. The protocol has been amended to reflect this.
Synopsis – Overall design, Section 1.2 Schema, Section 1.3 Schedule of Activities and Section 4.1 Study Design	The telephonic study exit visit at Day 30 was removed and Day 21 will now be the study exit visit.	Due to logistical reasons, and the fact that the drug is short acting with no known or projected long-term adverse events, the follow-up period was shortened.
Synopsis, Number of Subjects	Number of subject to be screened changed from 35 to 60.	The study center will use a 1:1 screen fail ratio. Therefore, up to 60 subjects will be screened to enroll 30.
Section 1.3 Schedule of Activities and Section 6.1 Study Treatment(s) Administered	Schedule of dose administration changed to every 7 hours, ie, a morning dose at 9:00 am, an afternoon dose at 16:00 pm and an evening dose at 23:00 pm.	Due to logistical reasons at the study center.
Section 1.3 Schedule of Activities and Section 8.2.7 Nasal and Epipharynx Endoscopy	Amend the protocol to allow for all pre-dose ear, nose and throat (ENT) procedures to be completed on Day -1 instead of Day 1. Removal of footnote for performing scoping within 4 hours of pre-dose on all other days so that there isn't a time constraint.	Due to logistical reasons at the study center as there will not be enough time to complete the ENT procedures on this day within window.
Synopsis, Objectives and Endpoints, Section 3.0	Plasma replaced with serum.	The table of endpoints was in error and listed plasma instead of serum as the detection matrix for biomarker analysis.
Section 5.2 Exclusion Criteria	Addition of exclusion criteria: "History of drug abuse or positive drug screening test at Screening or Day -1 prior to randomization".	Previously a urine drug screen was included in the Schedule of Activities, but no corresponding exclusion criteria existed.
Section 8.2.5 Otoscopy	Update to otoscopy assessments by removing mention of translucency and addition of colors to the section	Based on the update to the eCRFs regarding the otoscopy assessment, it was decided to update Section 8.2.5 of the protocol so that it matches the

Section # and Name	Description of Change	Brief Rationale
	preregarding the color of fluid behind the tympanic membrane.	way this procedure will be conducted and how the data will be collected.
Section 8.2.7 Nasal and Epipharynx Endoscopy	Updated assessments to be made when abnormal endoscopy is reported; additional criteria includes: swelling, redness, bleeding, rhinorrheoea (nose only) and other.	Based on the update to the eCRFs regarding the nasal and epipharynx endoscopy assessment, it was decided to update Section 8.2.7 of the protocol so that it matches the way this procedure will be conducted and how the data will be collected.
Section 8.2.9 Audiology Pure Tone Hearing Test and Appendix 10 Audiology Testing Template	Section 8.2.9 updated to refer to new Audiology Testing Template in Appendix 10	The Audiology Testing Template provided by the study center was used to develop the eCRF page. The template is attached as a sample source for reference.
Appendix 3, Table 8	Duplication of potassium and urea/blood urea nitrogen corrected.	Study center noticed duplication of potassium and urea in Table 8.

TABLE OF CONTENTS

PROTOCOL AMENDMENT SUMMARY OF CHANGES TABLE	3
TABLE OF TABLES.....	9
TABLE OF FIGURES.....	9
1.0 PROTOCOL SUMMARY	10
1.1 Synopsis.....	10
1.2 Schema	14
1.3 Schedule of Activities.....	15
2.0 INTRODUCTION.....	18
2.1 Study Rationale	18
2.2 Background	18
2.3 Benefit/Risk Assessment.....	19
3.0 OBJECTIVES AND ENDPOINTS	21
4.0 STUDY DESIGN.....	22
4.1 Overall Design	22
4.2 Scientific Rationale for Study Design.....	23
4.3 Justification for Dose	23
4.4 End of Study Definition.....	25
4.5 Dose-Escalation Criteria	25
4.6 Study Stopping Criteria	25
4.6.1 Stopping Criteria for Individual Subjects.....	25
4.6.2 Criteria for Stopping Dose-Escalation.....	25
4.6.3 Criteria for Stopping the Study.....	25
5.0 STUDY POPULATION	27
5.1 Inclusion Criteria	27
5.2 Exclusion Criteria	28
5.3 Lifestyle Considerations	30
5.3.1 Meals and Dietary Restrictions	30
5.3.2 Caffeine and Alcohol.....	30
5.3.3 Activity	30
5.4 Screen Failures.....	31
6.0 STUDY TREATMENT	32
6.1 Study Treatment(s) Administered.....	32
6.2 Preparation/Handling/Storage/Accountability	33

1.0 PROTOCOL SUMMARY

1.1 Synopsis

Protocol Title:

Evaluation of safety of repeated doses of OP0201 metered dose inhaler compared to placebo in healthy adult volunteers

Rationale:

OP0201 metered dose inhaler (MDI) (referred herein simply as OP0201) is a novel, intranasal drug device surfactant product being developed by Novus Therapeutics, Inc., for the treatment and prevention of otitis media (OM). To date, there is no drug product that has been approved to treat or prevent OM.

OP0201 is comprised of a 20:1 fixed combination of dipalmitoylphosphatidylcholine (DPPC; a phospholipid surfactant) and cholesteryl palmitate (CP; a neutral phospholipid spreading agent) suspended in propellant (HFA 134a). There are no other ingredients (ie, no excipients, no fillers) in the formulation other than the active ingredients and the propellant. None of these ingredients contain any animal or human derivatives. Both DPPC and CP are highly endogenous surfactants in humans, including the Eustachian tube (ET), nasopharynx and respiratory system. The drug product will be delivered as a local treatment through each nostril using a metered dose inhalation device. It will be sprayed directly backwards into each nostril by way of the anterior nostrils (not upwards towards the osteomeatal opening to the maxillary and ethmoid sinuses as other common intranasal products) towards the lateral wall of the nasal cavity so that the usual nasal mucociliary clearance pathway can facilitate delivery of the drug to the ET.

This Phase 1 safety study is designed to evaluate the safety and tolerability of daily intranasal OP0201 use for 14 consecutive days in 30 healthy adults. The study will be randomized, double-blind, placebo-controlled, parallel-group, and includes a dose-escalation cohort design with evaluation of 30 mg per day (Cohort A) and 60 mg per day (Cohort B) of OP0201.

For more information about OP0201, please refer to the most recent Investigator's Brochure (IB).

Objectives and Endpoints

Objectives	Endpoints
Primary	

 To evaluate the safety and tolerability of OP0201 30 mg per day (given as 2 sprays per nostril 3 times a day [TID] for 14 consecutive days) and OP0201 60 mg per day (given as 4 sprays per nostril TID for 14 consecutive days) compared to 0 mg placebo (HFA-134a only) administered in a similar parallel-group fashion TID for 14 consecutive days in healthy adult volunteers. 	
 Adverse events (AEs), otoscopy, tympanometry, nasal and epipharynx endoscopy, University of Pennsylvania Smell Inventory Test (UPSIT) olfactory test, audiology pure tone hearing test, triplicate 12-lead electrocardiogram (ECG), physical examination, vital signs, and clinical laboratory tests.

Secondary/Exploratory	

 • To evaluate if any systemic exposure of DPPC can be detected in serum at levels higher than endogenous DPPC levels in serum in up to 15 healthy adult volunteers who will be evaluated in the Cohort B dose (OP0210 60 mg per day) versus placebo. • To evaluate if any systemic exposure of CP can be detected in serum at levels higher than endogenous CP levels in serum in up to 15 healthy adult volunteers who will be evaluated in the Cohort B dose (OP0210 60 mg per day) versus placebo. 	
 • Maximum baseline adjusted serum concentration (C_{max}) of DPPC on Day 14. • Time to maximum concentration (t_{max}) of DPPC on Day 14. • Maximum baseline adjusted serum concentration (C_{max}) of CP on Day 14. • Time to maximum concentration (t_{max}) of CP on Day 14. • Additional parameters may be calculated, if appropriate.

Overall Design:

This is a randomized, double-blind, placebo-controlled, parallel-group, dose-escalation study in healthy volunteers to evaluate the safety and tolerability of OP0201 administered intranasally TID using a MDI compared to a matching placebo (HFA 134a minus active ingredients) administered intranasally TID using a MDI for 14 consecutive days. The plan is to enroll up to 30 subjects at 1 study center in the United States. Two dose cohorts are planned (Cohort A and Cohort B; N=15 per cohort). Within each cohort, subjects will be randomized in a 4:1 ratio to receive either OP0201 or placebo. After all subjects in Cohort A have completed the Day 14 visit, a Safety Review Committee (SRC) will review all the blinded safety data to determine whether the doses administered are safe and well tolerated. The SRC will make a recommendation to escalate to the next cohort (Cohort B) or not.

Potential subjects will be screened for eligibility during a screening period (Days -28 to -1). Eligible healthy volunteers will be admitted to the study center on Day -1 and be randomized on Day -1. Subjects will remain resident at the study center until after all the Day 15 assessments have been completed, with a study exit visit at Day 21.

Study treatment will be administered to the subjects by the study center staff TID for 14 days while resident at the study center.

The estimated duration of participation in the study for each subject is up to 54 days: Screening (Days -28 to -1), treatment (Day 1), 16-day residency (Days -1 to 15 with safety assessments at Days 4, 8, 14, and 15), study exit (Day 21 [+5 days]). No efficacy assessments will be performed for this study.

Number of Investigators and Study Centers:

Approximately 1 Investigator and study center are expected to participate in this study.

Number of Subjects:

Approximately 60 subjects will be screened to achieve 30 subjects randomly assigned to study treatment and 30 evaluable subjects for a total of 15 evaluable subjects per treatment group. Additional subjects may be screened to ensure a total of 15 evaluable subjects per treatment group. Subjects who are discontinued from the study may be replaced based on the Sponsor's discretion.

Treatment Groups and Duration:

Cohort	Dose Regimen	Cohort Dose Allocation		Total Subjects in Each Cohort	Total Subjects Per Dose Group
		Per Day Total Dose (mg)	Cumulative Total Dose (mg)		
A	2 sprays per nostril TID × 14 days	OP0201 (30 mg) ^a Placebo (0 mg)	OP0201 (420 mg) ^a Placebo (0 mg)	15	N=12 (OP0201) N=3 (Placebo)
B	4 sprays per nostril TID × 14 days	OP0201 (60 mg) ^a Placebo (0 mg)	OP0201 (840 mg) ^a Placebo (0 mg)	15	N=12 (OP0201) N=3 (Placebo)

a 2.5 mg per spray

N = number of subjects

Statistical Methods:Sample Size Determination

The sample size is not based on statistical considerations, but is typical for studies of this nature, and is considered adequate to characterize the distribution of the planned endpoints.

There will be a total of 30 subjects; 2 dose cohorts of 15 subjects each. Subjects will be randomized in 4:1 (OP0201:placebo) ratio to receive either OP0201 or placebo within each dose cohort.

Populations for Analyses

Entered Analysis Set All subjects who sign the informed consent form.

Safety Analysis Set All subjects who receive any study treatment (OP0201 or placebo). Subjects will be analyzed according to the treatment they received.

Pharmacokinetic (PK) Analysis Set All subjects in Cohort B who received at least 1 dose of OP0201 and have 1 quantifiable serum DPPC or CP concentration collected post-dose without important protocol deviations/violations or events thought to significantly affect the pharmacokinetics.

Statistical Analyses

The Statistical Analysis Plan (SAP) will be developed and finalized before database lock and will describe the subject analysis sets to be included in the analyses, and procedures for accounting for missing, unused, and spurious data. This section is a summary of the planned statistical analyses of the primary and secondary endpoints.

All analyses (with the exception of PK parameter analysis), summaries, and listings will be performed using SAS software (Version 9.4 or higher).

Pharmacokinetic Analyses

Pharmacokinetic analyses will be described in the SAP that will be finalized before database lock. All PK analyses will be performed on the PK Analysis Set.

Observed and baseline adjusted serum DPPC concentrations will be summarized by time point. Observed and baseline adjusted serum CP concentrations (if available) will be summarized by time point

Serum DPPC PK parameters (if any) will be summarized. Serum CP PK parameters (if available) will be summarized.

Safety Analyses

All safety analyses will be performed on the Safety Analysis Set.

Treatment-emergent adverse events (TEAEs) are defined as AEs that first occurred or worsened in severity after administration of study treatment.

Adverse events will be coded using the Medical Dictionary for Regulatory Activities (MedDRA). For each study treatment, numbers of TEAEs and incidence rates will be tabulated by preferred term and system organ class.

Treatment-emergent AEs by maximum severity, TEAEs by relationship to study treatment, serious adverse events (SAE), TEAEs leading to death, and TEAEs leading to discontinuation of study treatment will be tabulated for each study treatment.

All laboratory test results, vital signs measurements, and ECG results will be summarized for each treatment group using descriptive statistics at each visit for raw numbers and change from baseline.

Test results from otoscopy, tympanometry, nasal and epipharynx endoscopy, UPSIT olfactory test, and audiology pure tone hearing test will be listed and summarized as appropriate.

[figure not shown]
Safety Review Committee

After all subjects in Cohort A have completed the Day 14 visit, a SRC will review all the blinded safety data to determine whether the doses administered are safe and well tolerated and to make a recommendation to escalate to the next cohort (Cohort B) or not.

Data Monitoring Committee: Yes

1.2 Schema

Figure 1 Study Schema

1.3 Schedule of Activities

Table 3 Schedule of Activities

Study Period (with Visit Windows)	Screening Period	Confinement Period ^a (In-Clinic)							Study Exit	
		Day -1 (Admission)	Day 1 (Enrollment)	Day 4	Day 8	Day 14	Day 15	Day 21 (+5 Day) In-Clinic		
Informed Consent/Authorization	X									
Demographics	X									
Inclusion/Exclusion	X	X								
Pregnancy Test (Urine) ^c	X	X							X	X
Follicle Stimulating Hormone Test ^d	X									
Urine Drug Screen ^e	X	X								
Viral Serology ^f	X									
Medical, Surgical, Ear History	X									
Physical Examination ^g	X								X	X
Vital Signs ^h	X	X	X	X	X	X	X		X	X
12-Lead ECG ⁱ	X		X			X			X	X
Ear History	X									
Otoscopy ^j	X	X		X	X	X				
Tympanometry	X	X		X	X	X		X ^o	X ^p	
Nasal and Epipharynx Endoscopy ^k	X	X			X	X				
Clinical Laboratory Tests ^l	X					X				X
UPSIT Olfactory Test ^m	X				X	X		X ⁿ		X
Audiology Pure Tone Hearing Test	X					X		X ^o	X ^p	

Study Period (with Visit Windows)	Screening Period	Confinement Period ^a (In-Clinic)						Study Exit	
		Day -1 (Admission)	Day 1 (Enrollment)	Day 4	Day 8	Day 14	Day 15	Day 21 (+5 Day) In-Clinic	EaT ^b
Admission		X							
Train Participant on Study Product Administration ^q		X	X						
Randomization		X							
Study Treatment ^r			X	X	X	X			
Concomitant Medications	X	X	X	X	X	X	X	X	X
Adverse Events	X	X	X	X	X	X	X	X	X
PK Sample Collection			X ^r			X ^s			
Device Experience Questionnaire – Subject ^t							X		X ^u
Device Experience Questionnaire – Study Center Staff Administering the Treatment ^t							X		X ^u

EaT = Early termination; ECG = Electrocardiogram; IP = Investigational Product; PK = pharmacokinetic; UPSIT = University of Pennsylvania Smell Inventory Test.

- a Eligible healthy volunteers will be admitted to the study center on Day -1 and be randomized on Day -1. Subjects will remain resident at the study center until after all the Day 15 assessments have been completed.
- b EaT: To be performed if the subject was treated but early discontinue from the study.
- c For all females, urine pregnancy test must be negative to meet study enrollment criteria.
- d To be performed on postmenopausal women at Screening to confirm menopausal status (see [Appendix 6](#)).
- e Specific tests to be conducted are listed in [Table 8, Appendix 3](#).
- f To be performed at Screening only (see [Table 8, Appendix 3](#)).
- g Includes general appearance, overall status of the skin, head, neck, trunk, eyes, heart and lungs (eg, breathing sounds), abdomen, extremities, lymph nodes. Height and weight are recorded only at the Screening visit.
- h Vital signs include blood pressure, respiratory rate, pulse rate, and body temperature.

- i A single 12-lead ECG will be collected for screening purposes. For subjects in Cohort A, a single 12-lead ECG will be collected on Day 1 prior to the first dose and on the study exit visit (Day 21). For subjects in Cohort B, triplicate ECGs will be collected on Day 1: 30 and 60 minutes prior to the first dose, Day 14: 30 minutes prior to the last dose and 5, 20, 35, 50 minutes following the last dose on Day 14. In cases where ECG and PK sampling overlap, ECGs should be collected first, to ensure that PK samples are collected at the scheduled time point.
- j Otoscopy involves ear endoscopy, taking a picture of the tympanic membrane and assessing if there are any abnormal findings.
- k Nasal endoscopy will include a measurement of nasal cavity length (in mm) at the Screening visit only. For all other scheduled assessments, the nasal and epipharynx endoscopy assessment should be done prior to the first dose of the day.
- l Includes hematology, clinical chemistry, coagulation and urinalysis (see [Table 8, Appendix 3](#)).
- m At Screening, a total UPSIT score of ≥ 35 (for females) and a total UPSIT score of ≥ 34 (for males) is required to meet study enrollment criteria.
- n To be collected at the Day 21 study exit visit only if abnormal at the Day 14 visit. Abnormal is defined as UPSIT score < 35 (for females) and < 34 (for males) (see [Section 8.2.8](#)).
- o Audiology pure tone hearing test if abnormal in either ear at Day 14 visit. Abnormal defined as > 20 dB worsening from baseline at Day 14 visit ([Rosenfeld et al, 2004](#)). Typanometry is performed along with the Audiology pure tone hearing test so if the subject requires a hearing test at this visit, tympanometry will also be performed.
- p Audiology pure tone hearing test and tympanometry not required if subjects drops out before Day 14, but if they drop out after Day 14 and had an abnormal test result at Day 14 visit, then every effort should be made to have the patient complete these assessments at the EaT visit.
- q Study subjects need to be trained on study treatment administration on Day -1 or on Day 1, prior to the first dose.
- r Study treatment dosing recommendation: the first dose at 9:00 am, second dose at 16:00 pm and the third dose at 23:00 pm.
- s PK sample timing Cohort B only: Day 1: 30 and 60 minutes prior to the first dose, Day 14: 30 minutes prior to the last dose and 5, 20, 35, 50 minutes following the last dose on Day 14. The 5-minute PK sample should be collected within ± 2 minutes of the scheduled time and the 20-minute PK sample should be collected within ± 5 minutes of the scheduled time. All other PK samples should be collected within ± 5 minutes of the scheduled time.
- t To be completed before discharge from the study center on the morning of Day 15 (See [Appendix 7](#) for an example).
- u This assessment is needed only if subjects discontinue the study prior to completing the questionnaire on Day 15.

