6.1 Study Treatment(s) Administered

The following study treatments will be used in this study.

Study Treatment #1: OP0201

OP0201 is an intranasal aerosol, a dosage form recognized by the US Pharmacopeia, that is comprised of 2 active ingredients, DPPC and CP, in approximately 20:1 (w/w) ratio, suspended in an inactive ingredient, the synthetic chlorofluorocarbon-free propellant HFA 134a. All OP0201 ingredients are synthetic; none of these ingredients contain any animal or human derivatives. OP0201 is supplied in mechanical packing parts that includes a pressurized canister with a securely attached metering valve where the drug product is contained, an actuator into which the canister is seated and the valve connects with device body, and a tip to deliver the drug to the nostrils.

OP0201 is manufactured using Good Manufacturing Processes (GMP) with development phase appropriate compliance with global Health Authority guidelines (eg, [US FDA Guidance for Industry: Nasal Spray and Inhalation Solution, Suspension and Spray Drug Products, July 2002](#)) by [REDACTED]. The OP0201 canisters are filled to deliver 100 actuations (sprays) per canister. Each MDI spray of OP0201 delivers 0.1 mL of HFA-134a containing a total of 2.5 mg of the active pharmaceutical ingredients as dry powder suspended in the HFA-134a.

See the IB for further details regarding OP0201.

Study Treatment #2: Placebo

The placebo is comprised of the same synthetic chlorofluorocarbon-free propellant, HFA-134a, an inactive ingredient as used in the study treatment #1 described above. The placebo is manufactured using GMP with development phase appropriate compliance with global Health Authority guidelines (eg, [US FDA Guidance for Industry: Nasal Spray and Inhalation Solution, Suspension and Spray Drug Products, July 2002](#)) by [REDACTED].

The placebo canisters are filled to deliver 100 actuations (sprays) per canister. Each 0.1 mL MDI spray of placebo delivers 0.1 mL of HFA-134a.

For each dose, the subject will have administered to them by the study center staff, 2 (Cohort A) or 4 (Cohort B) consecutive sprays first to the left nostril and then to the right nostril for a total of 4 (Cohort A) or 8 (Cohort B) sprays (see Study Manual for Study Treatment Instructions for Use). The dose will be repeated 3 times a day for a total of 14 days (42 doses).

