The study treatment will be administered every 7 hours: a morning dose at 9:00 am, an afternoon dose at 16:00 pm and an evening dose at 23:00 pm. The Investigator or qualified designee will record each dose by noting the time and number of total sprays administered successfully in a dosing log.

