7.5. BASELINE

Baseline is defined as the last scheduled non-missing measurement taken prior to dosing and will

Document: Statistical Analysis Plan
Author: [REDACTED]

Version Number:
Version Date:

2.0
03APR2019

correspond to: Screening assessment for clinical laboratory; Day -1 assessment for Vital Signs; Day 1 pre-dose assessment for ECG in Cohort A, and the average of the mean triplicate ECG assessments at Day 1, 60 minutes pre-dose and Day 1, 30 minutes pre-dose for ECG in Cohort B; Screening assessment for Physical Examination; Day -1 assessment for Otoscopy, Tympanometry, and Nasal and Epipharynx Endoscopy ; and Screening assessment for University of Pennsylvania Smell Inventory Test (UPSIT) Olfactory test, and Audiology Pure Tone hearing test. However, if a subject is missing the planned baseline collection then the last non-missing evaluation prior to dosing (scheduled or unscheduled), if available, will become the baseline value.

For PK assessments, baseline serum concentration is defined as the mean of the two predose serum concentrations observed in samples collected on Day 1 prior to the first dose. If one predose sample is missing, the other Day 1 predose concentration will be used for baseline correction.

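### Cohort B's DPPC and ECG baselines are morning values set against late-evening Day 14 values, and protocol and SAP disagree on whether placebo Day 14 PK samples are assayed

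*Protocol*

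**What the plan says.** **Dosing clock.** Protocol 6.1 sets "a morning dose at 9:00 am, an afternoon dose at 16:00 pm and an evening dose at 23:00 pm". Footnote r of the Schedule of Activities gives the same times but calls them a recommendation.

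**PK sampling.** Footnote s has "PK sample timing Cohort B only: Day 1: 30 and 60 minutes prior to the first dose, Day 14: 30 minutes prior to the last" (the 23:00 dose), then 5, 20, 35 and 50 minutes after it.

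**Cohort B ECGs.** Footnote i has "triplicate ECGs will be collected on Day 1: 30 and 60 minutes prior to the first dose, Day 14: 30 minutes prior to the last" (again the 23:00 dose), with the same four post-dose times.

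**Baselines.** SAP 7.5 states that "baseline serum concentration is defined as the mean of the two predose serum concentrations observed in samples collected on Day 1 prior to the first" administration. The Cohort B ECG baseline is likewise the average of the two Day 1 pre-dose triplicate means.

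**Endpoints.** SAP 3.2 takes baseline-adjusted Day 14 Cmax and its time for DPPC. SAP 4.3 reports that CP cannot be quantified, so DPPC is the only analyte left. SAP 17.8 summarises ECG change from baseline, and SAP 17.8.1 counts QTcF increases above 30 and 60 ms.

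**Placebo PK samples.** Protocol 8.5.2 assays placebo baseline samples but not those drawn after dosing, and Protocol 9.3 limits the PK set to subjects given OP0201. SAP 6.3 admits placebo subjects with a quantifiable post-dose DPPC value, and SAP 16.1 and 16.2 summarise by treatment. SAP 4.3 does not list this as a change from the protocol.

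**Meals.** Protocol 5.3.1 restricts certain fruit products. Neither document sets a fasting rule, meal time or standard meal around sampling.

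**The concern.** The secondary objective asks whether serum DPPC rises above its endogenous level. The planned measure subtracts an early-morning level from late-evening levels two weeks later. Anything that moves endogenous DPPC between morning and night is then reported as exposure if it is a rise, or hides exposure if it is a fall. A placebo group sampled on the same evening would separate the two, and Protocol 8.5.2 removes that group from the assay.

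The Cohort B ECGs follow the same clock. A subject's QTcF change from baseline therefore contains whatever QTcF does between about 08:15 and 23:00 without drug, and the counts above 30 and 60 ms are made subject by subject from that change.

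**Working it through.** **1. The plan's own dosing figures.** 09:00 + 7 h + 7 h = 23:00. 3 doses x 14 days = 42 doses. Both reproduce: the last dose is at 23:00 on Day 14, after 41 earlier doses.

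**2. Clock times from footnotes i and s.**

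| Measurement | Offset | Clock time |
|---|---|---|
| Day 1 baseline | 60 min before first dose | 08:00 |
| Day 1 baseline | 30 min before first dose | 08:30 |
| Day 14 | 30 min before last dose | 22:30 |
| Day 14 | 5 min after | 23:05 |
| Day 14 | 20 min after | 23:20 |
| Day 14 | 35 min after | 23:35 |
| Day 14 | 50 min after | 23:50 |

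Smallest gap: 22:30 - 08:30 = 14.0 h. Largest: 23:50 - 08:00 = 15.8 h. The sampling windows are only minutes wide and do not alter this.

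**3. What each difference contains.** Let E be the evening-minus-morning change in endogenous DPPC, A the residue of the first 41 doses, and L the increment from the last dose. Treat E as constant between 22:30 and 23:50, and read the correction as Day 14 minus baseline. (The wording in SAP 16.1 literally runs the other way and needs separate correction.)

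- Active, post-dose minus Day 1 baseline: E + A + L
- Active, 22:30 minus Day 1 baseline: E + A
- Active, post-dose minus 22:30: L
- Placebo, Day 14 minus Day 1 baseline: E

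Active data alone give L, but cannot split E from A. The placebo line is the one that does, and it exists only if the placebo Day 14 samples are assayed.

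**4. How far E reaches Cmax.** This is an illustrative simulation with no absorption. Baseline is the mean of two samples, Cmax is the largest of four post-dose differences, and negative values are set to zero as in SAP 16.1. Independent normal errors with within-subject SD 1, and the shifts themselves, are assumptions.

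| Evening shift E (SD) | Mean Cmax (SD) | Increase over no shift |
|---|---|---|
| 0 | 1.10 | - |
| 0.5 | 1.55 | 0.45 |
| 1 | 2.04 | 0.94 |
| 2 | 3.03 | 1.93 |

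An evening rise passes almost one-for-one into Cmax. Even with no shift, mean Cmax is above zero, so it cannot be judged against zero without a control.

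**5. Precision of the time-matched contrast (12 v 3).** SE = SD x sqrt(1/12 + 1/3) = 0.645 SD. With 13 df, t = 2.160, so the 95% half-width is 2.160 x 0.645 = 1.39 SD. The same figure applies to the Day 14 ECG contrast. Cohort A placebo subjects add nothing on Day 14, because footnote i gives them ECGs only at screening, Day 1 and Day 21.

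**6. After moving the baseline to 22:00 and 22:30 on Day -1.** The gap runs from 22:30 - 22:30 = 0 h to 23:50 - 22:00 = 1.8 h.

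**The case against.** The best defence is that the plan already holds time-matched information. Under SAP 6.3 the three Cohort B placebo subjects form an evening control. Observed concentrations are summarised as well as adjusted ones, and the 22:30 sample is a same-evening reference. Placebo ECGs share the active schedule and allocation is randomised. PK is secondary or exploratory, no hypothesis is tested, and Protocol 4.3 doubts that systemic levels matter. Footnote r calls the dose times a recommendation, and Protocol 8.5.1 allows sample times to be adjusted.

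Much of this stands, and it rules out several stronger readings that a reader might infer:

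- *That the DPPC comparison is confounded whatever is done.* It is so only if Protocol 8.5.2 governs. If SAP 6.3 governs, the problem becomes one of precision.
- *That the adjusted difference is the only exposure measure.* Observed levels are also reported (Protocol 9.4.2, SAP 16.1).
- *That the ECG comparison with placebo is confounded.* It is time-matched, though very imprecise.
- *That meals differ between the two occasions.* Meal timing is unspecified, not shown to differ, and the Laboratory Manual is not available here.
- *That the artefact can be sized in concentration units.* The documents give no endogenous level, within-day change or clearance. The content of one dose is no ceiling after 41 earlier ones.

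Three things remain. The 22:30 sample isolates only the last dose. Protocol 6.1 states the dose times firmly, and nothing in either document plans a time-matched baseline. Individual QTcF changes get no protection from a placebo group, and SAP 17 plans no between-group safety comparison unless a section specifies one.

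**Conclusion.** The clock-time mismatch is certain on the nominal schedule: 14.0 to 15.8 hours for every Cohort B baseline-to-Day 14 comparison. Its effect on DPPC and QTcF is unknown, because the documents give no within-day figures.

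For PK, baseline-adjusted Cmax mixes time of day with 14 days of dosing. Under Protocol 8.5.2 no control separates them. Under SAP 6.3 they can be separated, with a 95% half-width of about 1.39 SD (normal theory, equal variances, all 15 subjects contributing). SAP 7.1 requires three values for full descriptive statistics, so losing one placebo subject would reduce that column to its minimum and maximum.

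For ECG, only within-arm change from baseline and the individual QTcF-change counts are affected.

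The plan should be changed. The point does not touch the remaining safety endpoints, but it weakens the one PK objective that is still feasible, and the remedy is cheap.

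**What to change.** 1. **Match the clock.** Take the two Cohort B baseline PK samples and triplicate ECGs at about 22:00 and 22:30 on Day -1, when subjects are already resident, with the same interval from the last meal as on Day 14. Update Protocol Table 3 with footnotes i and s, the sampling days in Protocol 8.5.1, SAP Table 2, SAP 7.5, SAP 16.1 and 16.2, and the nominal times in SAP Appendix 1.
2. **Settle the placebo samples.** Reconcile Protocol 8.5.2 and 9.3 with SAP 6.3, and record the outcome in SAP 4.3. Assay the placebo Day 14 samples and report active beside placebo at matched times. Add change from the 22:30 sample as a supplementary summary, labelled as describing the last dose only.

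**Cost.** Evening work on Day -1, no Cohort B ECG immediately before the first dose, and assays for three placebo subjects (3 x 5 = 15 Day 14 samples at most) on blood the schedule already collects. No samples or tracings are added. If Cohort B sampling has already taken place, step 2 is still open provided the samples are within the stability limits that Protocol 8.5.2 requires.
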